A new closure technique of OCA closure using a self-adhering mesh (Dermabond Prineo®) was developed that further decreased operative times and had similar outcomes. Parvizi et al showed benefits including that patients could shower immediately, could be removed easily with less pain after healing, forms a microbial barrier, provides even tension distribution across the wound, and reduced subcutaneous closure time compared to monocryl with steri strips [13]. Additionally, since the time in the operating room was less, the Prineo was found to be overall less expensive [13]. Richter et al also showed that while Prineo provided equivalent skin approximation compared to intradermal sutures, it was 4.5 times faster to apply and resulted with similar incision healing and cosmetic outcomes [14]. With positive results seen in the literature, Prineo dressings have been increasingly used in total hip and knee replacements. Holte et al evaluated a 2.5 year period with 360 consecutive primary total knees by one surgeon and showed that use of Prineo was successful for high tension total knee wounds, with no cases of wound dehiscence, operative intervention, or prosthetic joint infection [15]. Sutton evaluated the cost-effectiveness of Prineo compared to skin staples and found that Prineo was associated with a shorter length of stay, fewer discharges to rehab, and lower rates of allcause readmission [16].

The goal of this study is to compare conventional methods of wound closure after total shoulder arthroplasty, such as monocryl and dermabond, to a OCA mesh closure technique and evaluate its success.

Objective and Hypothesis:

The objective is to compare two types of wound closure after total shoulder arthroplasty to determine which closure is faster, and subsequently if there are different outcomes between the two types of closures.

The objective of this study is to compare two types of wound closure after total shoulder arthroplasty procedures. A single fellowship trained shoulder surgeon will perform all procedures. We hypothesize that patients who undergo an OCA mesh closure will have a faster closure time, lower cost, non-inferior complication rate, and non-inferior patient satisfaction scores with respect to their postoperative follow up and scar appearance.

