Patients in the OCA mesh cohort will be compared to patients who have a closure with a running monocryl suture and dermabond. This investigation seeks to determine if OCA closure mesh closure is non-inferior to monocryl suture and dermabond in terms of operative time, cost, complications, and aesthetic appearance.

If the hypothesis is confirmed, this study will suggest that a OCA mesh closure may be used for total shoulder arthroplasty surgeries as an alternative to current conventional closures and may provide a cost benefit.

Specific Goal:

1) To specifically be able to make a recommendation of total shoulder wound closure based on complications, aesthetic result, time to closure, and cost

Specific Aims:

- 1) To compare the timing of total shoulder closure between OCA mesh and monocryl/dermabond closure
- 2) To compare the costs of the OCA mesh closure versus monocryl/dermabond
- 3) To compare the complications the OCA mesh closure versus monocryl/dermabond closure
- 4) To compare the healing and patient satisfaction of wounds between the OCA mesh closure versus monocryl/dermabond closure

Study Plan:

The study will be implemented at the Wakefield Campus of Montefiore medical center by randomizing patients undergoing total shoulder arthroplasty to receiving closure with monocryl and dermabond versus dermabond with self-adhering mesh. Participants will be subsequently followed for 3 months to evaluate wound healing and monitor for complications.

Methods:

- Design Prospective randomized intervention
- Setting Wakefield Hospital of Montefiore Medical Center
- Participants Patients who agree to participate in the study undergoing total shoulder arthroplasty
- Study Period
 - \circ Sample size 22 patients
 - Determine using a standard between-groups sample size calculation with a type 1 error rate of 5% and 80% power to detect a moderate effect size (0.5 standard deviation)
 - o Inclusion
 - Total shoulder arthroplasty
 - Reverse total shoulder arthroplasty

- Age 18-100
- Single Surgeon
- o Exclusion
 - Previous shoulder surgery
 - Known wound healing complications
 - DM, chronic steroid use, vascular insufficiency, morbid obesity (BMI>40), ESRD, family hx of pathologic scars
 - Patients on blood thinners (ASA 81mg ok)
 - Connective tissue disease
 - Allergy to skin adhesive
 - Mentally unable to complete questionnaires
 - Previous wound over planned incision
- Measures
 - o Time for closure
 - Cost of closure (time in OR, materials)

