 - Wound cosmesis
 - Patient and Observer Scar Assessment Scale (POSAS)
 - Wound complications (i.e. dehiscence)
 - Wound drainage
 - Infection (superficial vs. deep)
 - Length of stay in hospital
- Endpoints
 - o Primary endpoint is to determine which method of closure is faster
 - Secondary endpoints will include cost of closure, difference in wound complications, aesthetic differences, and difference in patient satisfaction
- Independent Variables
 - o Age
 - o BMI
 - o Race
 - o Gender
 - Length of Incision
 - Depth of Incision
 - o Prealbumin
 - o Albumin
 - o Glucose
- Randomization and blinding
 - A random number generator will be used to assign patients to the study and control groups. Patients will not be notified which group they had been assigned to, though they may be able to determine which group they are in after looking at their wound.

Study Protocol:

20 total shoulder replacement patients presenting to Wakefield Medical Center will be screened for eligibility according to the inclusion and exclusion criteria by study personnel. Medical history and demographic data will be collected and assessed to ensure

that patients meet the inclusion and exclusion criteria. Eligible subjects will be enrolled after informed consent is obtained.

- Prospective Randomized Design
 - After determining a patients' eligibility for inclusion, they will be randomized to the OCA mesh group or monocryl with dermabond group. After surgery, both groups will be seen at their 2 week, 6 week, and 3 month appointment.
- Surveys
 - At the 6 week, and 3 month follow up appointment both groups and the same surgeon will complete a patient observer and scar assessment scale survey
 - The Patient Observer and Scar Assessment Scale validated instrument created to measure patients and physician overall satisfaction with surgical wound appearance / healing [17]
- Data Collection

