 - For each enrolled subject, we will collect data from hospital presentation to discharge on standard demographics, routine laboratory results, clinical information, past medical history and hospital course data (length of stay, mobilization status, associated inpatient procedures and complications). Major complications are defined as: all-cause re-hospitalization, re-hospitalization relating to index surgery, DVT, PE, deep wound infection, dislocation, fracture, death. Minor complications include: UTI, delayed wound healing, superficial wound infection. Complications resulting from the surgery will be distinguished from those resulting from pre-existing conditions and comorbid states.
 - All the data will be recorded and stored in a password-protected Excel spreadsheet on study personnel password-protected work computers.
- Statistical Considerations
 - o Power Analysis
 - Power Power analysis (IBM SPSS 21) was performed before the study at a level of 0.05 alpha error and 0.8 beta error. Looking at closure time of total shoulder arthroplasty wounds, looking for an effect size of 13 minutes between closure groups determined that a sample size of 2 patients in each group was adequate to detect significant differences in closure times between groups. Increasing group size to 5 patients in each group resulted in a power of 88% at an alpha of 0.05 and using 10 patients in each group resulted in 100% power at an alpha of 0.05.

Measures to address study aims:

To address specific aim 1: We will first measure the length of the incision and depth of the wound with a intraoperative flexible ruler prior to closure. We will assess the timing of closure in the operating room by the surgeon announcing the start of closure. At this time, the circulating nurse will start monitoring time with a stopwatch. Once the dressings are completely on, the surgeon will announce to end time and the circulating nurse will stop the stopwatch. The timing of closure will be recorded.

To address specific aim 2: We will compare the costs of the two closure methods by determining the cost of the medical supplies used for closure, as well as calculating the cost of the operating room time that was required for each closure. The sum of these costs will be the total cost of closure.

To address specific aim 3: We will compare complications, including drainage and infection, between the groups over a 3 month period.

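### The primary closure-time clock starts on an unanchored call by the one operating surgeon, and nothing in the plan keeps the allocation from that surgeon until the call

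*Combined protocol and SAP*

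**What the plan says.** The Endpoints list states: "Primary endpoint is to determine which method of closure is faster". How time is measured is set out under Measures to address study aims, specific aim 1, in this order:

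- Before closure: "We will first measure the length of the incision and depth of the wound with a intraoperative flexible ruler prior to closure".
- Start: "We will assess the timing of closure in the operating room by the surgeon announcing the start of closure". Then: "At this time, the circulating nurse will start monitoring time with a stopwatch".
- Stop: the surgeon calls the end once all dressings have been applied, and the nurse stops the watch.

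Specific aim 2 uses the same interval again, because the cost of closure includes "calculating the cost of the operating room time that was required for each closure".

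Under Objective and Hypothesis the plan says: "A single fellowship trained shoulder surgeon will perform all procedures". The same section gives the hypothesis that mesh closure is faster and cheaper. Mesh patients "will be compared to patients who have a closure with a running monocryl suture and dermabond".

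The Study Protocol section places randomisation after eligibility is established, and Informed Consent places consent before the day of surgery. Randomization and blinding names a random number generator and says that patients are not told their group. It does not say when the surgeon learns the arm.

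**The concern.** The stop has an observable anchor and the start has none. No layer, stitch or instrument step is named, and the ruler measurement fixes an order of events without starting the clock. The nurse holds the watch but acts on the surgeon's word, so a separate timekeeper does not make the start independent.

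The person giving that word performs every case in a trial whose hypothesis is that mesh is faster. Nothing in the documents withholds the arm from that person beforehand. A start called slightly later in mesh cases, or slightly earlier in control cases, would favour mesh without anyone intending it.

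At stake is the size of the time difference, and through it the cost comparison. Both feed the stated goal of recommending a closure method partly on time and cost.

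**Working it through.** **1. Start against stop.** Both are spoken by the surgeon. The stop follows a state that anyone in the room can see. The start follows no named state. The only observable step near it that is common to both arms is the recording of length and depth, and the clock is not linked to it.

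**2. Who knows the arm, and when.** Randomisation follows eligibility, and consent precedes the day of surgery, so the allocation may exist before the operation. No sealed envelope or intraoperative reveal is described. The text is silent on the surgeon's knowledge in both directions.

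**3. How an arm-dependent call enters the results.** Let b be the between-arm shift in the start call, in minutes, and r the operating room cost per minute (not given).

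- Observed time difference = true difference + b.
- Observed cost difference = true cost difference + b × r.

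Against the 13 minutes in the Power Analysis, assumed shifts of 1, 2 and 3 minutes are 1/13 = 8%, 2/13 = 15% and 3/13 = 23%.

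**4. Illustrative false-positive rates.** No SD, test or shift is given. I assume a two-sided t-test at 0.05, 11 per arm (the 22 patients in Methods, split equally) and b = 2 minutes. Three planning statements each imply an SD:

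- 88% power at 5 per group for 13 minutes: solving the noncentral t power equation gives SD 5.73.
- 2 per group called adequate, read as 80% power for 13 minutes: SD 2.3.
- 13 minutes read as the moderate effect of 0.5 SD in Methods: 13/0.5 = SD 26.

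These do not agree. SD 5.73 reproduces 88% at 5 per group but gives only 26% power at 2 per group. I therefore show all three.

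With no true difference, the rejection rate is P(|T| > 2.086), where T is noncentral t with 20 degrees of freedom and noncentrality b / (SD × √(2/11)), and √(2/11) = 0.426.

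| SD (min) | Noncentrality, b = 2 | False-positive rate |
|---|---|---|
| 2.3 | 2/(2.3 × 0.426) = 2.04 | 49% |
| 5.73 | 2/(5.73 × 0.426) = 0.82 | 12% |
| 26 | 2/(26 × 0.426) = 0.18 | 5% |

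At SD 5.73, shifts of 1 and 3 minutes give about 7% and 22%. With 10 per arm (the 20 patients in the Study Protocol section), the 2-minute figure at SD 5.73 is 11.5%.

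**5. If the true difference is near 13 minutes.** At SD 5.73 and 11 per arm, power for 13 minutes is already 99.9%, so a shift of a few minutes has almost no room to change the test result. At SD 26 the power is only about 20%, but a finding of faster would still point the right way. In both cases the damage is to the estimated size.

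**The case against.** **The primary question is only a direction.** Near 13 minutes a small shift does not decide which method is faster, and the false-positive rates need a true difference near zero. This stands. It limits the harm to the size of the time difference and the aim 2 cost.

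**The figures are not anchored in the documents.** The shifts are assumed, and the planning statements imply SDs from 2.3 to 26 minutes. This stands too. The table shows how wide the uncertainty is; the point itself rests on the text.

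**The start is less open than it looks.** Length and depth come first, and measuring depth before closure suggests that the wound is still open when the clock starts. That is fair, but it bounds the start on one side only. The gap between the measurement and the call remains at the surgeon's discretion.

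**Concealment is argued from silence.** A reader might infer that the surgeon will know the arm, or that closure times will in fact be biased. The documents support neither; they show only that nothing prevents it. Nor does the password-protected randomisation file help either side. It appears as a confidentiality measure, and names were removed from the public text, so its holder cannot be used as evidence.

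**The remedy is partial and has costs.** Revealing the arm in theatre can put kit preparation inside the clock. An unmasked surgeon still sets the closure speed and calls the stop. Both are true. The change closes the start-time path only.

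**Conclusion.** The point holds in a limited form and is worth correcting. The start of the primary measurement is an unanchored call by the single surgeon, and the plan does not withhold the arm before it. An arm-dependent call would bias the time difference and the operating room cost minute for minute: 8% to 23% of 13 minutes for assumed shifts of 1 to 3 minutes.

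A reader might conclude that the gap could manufacture the finding that mesh is faster. Near the planned 13 minutes it would not do so by itself. A false finding needs a true difference near zero, and its probability under a 2-minute shift could be anywhere from about 5% to 49%, depending on an SD that the documents do not give. The gap in the procedure is certain on the text; whether any shift would occur, and how large, is unknown.

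**What to change.** Amend specific aim 1 under Measures to address study aims:

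1. The circulating nurse starts the stopwatch when incision length and wound depth have been recorded. This step is already planned for every patient, is the same in both arms and comes before any closure step.
2. The allocation stays sealed until that moment and is then revealed.
3. The clock runs from there to the existing stop, when all dressings have been applied.
4. Optionally, the nurse records a split time at the start of skin closure.

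The nurse, stopwatch and ruler are already in the plan. The added costs are:

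- one sealed allocation per patient, and both kits in the room unopened;
- a few seconds for the reveal;
- any kit preparation not done in parallel falls inside the clock, and so inside the aim 2 cost;
- closure steps common to both arms are counted, which adds some variance. The split time lets the skin-closure part be shown separately.

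The protocol should also say that the surgeon is unmasked after the reveal, so closure speed and the stop call stay open to influence.

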Confidentiality will be protected by assigning a unique masked ID that will be linked to subjects' identifiers (e.g., name).

Storing documents in hard copy:

Any documents that contain PHI (e.g., consent forms, link between the ID to subjects' identifiers, de-identified research documents) will be stored in a locked cabinet within the office of [name]. IRB-approved study personnel will be the only individuals with access to any research documents containing PHI.

Storing Documents Electronically

Any documents that contain PHI (e.g., consent forms, subject identifier/deidentifier table) will be stored in a password protected computer document on the primary investigator's desktop computer. Only IRB approved personnel will be the only individuals with access to any research documents containing PHI. Randomization information will be kept in a password-protected file on the computer of [name].

Storing Documents on Portable Electronic Devices

No PHI or research data will be stored on any portable electronic devices (e.g., laptops, tablets, flash drives, etc.)

Emailing Data

Any research data that will be emailed will be de-identified and encrypted according to Montefiore Medical Center ITS department standards. PHI will not be emailed to any commercial email addresses.

Potential Benefits

The proposed potential benefits of this study may include faster surgical times, decreased operative costs, equivalent or improved complication rates, and improved patient satisfaction. There is evidence to support OCA mesh closure is faster and has similar complications.

Follow-up procedures

The data collection period for each patient will begin during the preoperative visit and end after each patient completes the in clinic 3-month follow up visit and study surveys patient reported outcome scores will be followed indefinitely.

Early termination/discontinuation of the study protocol

Once enrolled, patients may elect to discontinue participation in the study at any time, as per the language set forth in the consent document. Note: if randomized and subjects opt out afterwards, they will be in the intention to treat category. Patients who elect to leave the study will not be followed further and their data will be managed in an appropriate fashion.

Data and Safety Monitoring

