The signed assurances of the PI ([name]) included in the CCI/IRB Research Application form, including the policy for reporting internal and external adverse events should constitute a sufficient plan. Additionally, as a single site and small numbers of study subjects, close monitoring every 3 months by the study investigators ([name] and [name]) should be adequate as well. An independent data safety monitor will be appointed..

Project Management

[name] – Primary Investigator – will be responsible for the research protocol, study implementation plan, obtaining consent from eligible patients, and data analysis and interpretation

[name] – Primary Resident Investigator – will be responsible for the research protocol, study implementation plan, subject screening, obtaining consent from eligible patients, data collection and analysis, and coordination between different departments and ancillary services.

[name] – Secondary Resident Investigator - will be responsible for the research protocol, study implementation plan, subject screening, obtaining consent from eligible patients, data collection and analysis, and coordination between different departments and ancillary services.

Expected Outcomes

The expected Outcomes of this randomized prospective study is faster closure times and non-inferior complication rates with equivalent patient satisfaction for the OCA mesh group compared to the conventional closure group. There is no expected increase in adverse outcomes for the OSA mesh group.

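### The protocol sets out no allocation concealment: nothing makes the holder of the randomisation file independent of enrolment, and nothing delays release of the assignment until the wound has been measured

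*Combined protocol and SAP*

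**What the plan says.** **Generation.** Methods, under Randomization and blinding: "A random number generator will be used to assign patients to the study and control groups". The only masking described there is that patients are not told their group, and the text accepts that they may work it out from the wound.

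**Timing.** Study Protocol: "Eligible subjects will be enrolled after informed consent is obtained". Under Prospective Randomized Design: "After determining a patients' eligibility for inclusion, they will be randomized to the OCA mesh group or monocryl with dermabond group". The Informed Consent section places consent before the day of surgery.

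**Custody.** Confidentiality of Research Records, Storing Documents Electronically: "Randomization information will be kept in a password-protected file on the computer of" a person whose name is removed from the public copy.

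**Who enrols.** Project Management lists three roles. The primary investigator's duties include "obtaining consent from eligible patients, and data analysis and interpretation". Each of the two resident investigators has "subject screening, obtaining consent from eligible patients, data collection and analysis".

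**The endpoint and its measurement.** The primary endpoint is which closure is faster. One surgeon performs every procedure. Under specific aim 1, incision length and wound depth are measured during the operation before closure; the surgeon then announces the start and end of timing, and the circulating nurse runs the stopwatch.

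**The concern.** Random generation protects a comparison only if the people who decide who enters the trial, and how the case is set up, cannot act on the next assignment. Here the surgeon cannot be blinded to the closure, calls both ends of the timed interval, and works under a protocol whose hypothesis is that mesh is faster. Concealment is therefore one of the few safeguards still available, and the plan does not describe any.

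Two separate routes to bias are left open:

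- **Selection at enrolment.** A recruiter who knows or can find out the next arm could hasten, delay or discourage entry on the basis of features visible before surgery, such as BMI.
- **Conduct after assignment.** A surgeon who knows the arm before the incision could, even without intending to, make it longer or shorter, or deeper or shallower. This is not selection, since the patient is already in the trial, but it acts on the same endpoint.

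The protocol lists BMI, incision length and incision depth as independent variables but specifies no analysis that adjusts for them. With 20 to 22 patients in total, a few influenced cases could move a group mean.

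**Working it through.** **Step 1: what the text establishes.** This part needs no arithmetic. The sections on randomisation, storage, consent and roles were set against what a concealment procedure has to state.

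| Question | Answer in the documents |
|---|---|
| How is the sequence generated? | Random number generator; no allocation ratio, blocking or stratification given |
| Is a list made in advance, or is a number drawn per patient? | Not stated |
| Who generates it? | Not stated |
| Where is it kept? | Password-protected file on one person's computer |
| Who knows the password? | Not stated |
| Is the holder independent of screening, consent and surgery? | Not stated |
| When is an assignment released, and to whom? | After eligibility; nothing more |
| Envelopes, central service or independent custodian? | None described |

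Of the three roles listed, 3 of 3 obtain consent and 2 of 3 also screen. None is described as independent of recruitment. Restoring the masked name would show who holds the file, but it would not supply a procedure.

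**Step 2: which route can act on which variable.** Consent comes before the day of surgery, and incision length and depth are measured in the operating room. A recruiter therefore cannot select on wound dimensions, only on features visible before surgery. The surgeon can influence the wound dimensions, because nothing holds back the assignment until after the incision.

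**Step 3: illustration of scale.** The plan gives no SD for closure time, so one is back-calculated from its Power Analysis: a 13-minute difference, two-sided alpha 0.05 (two-sidedness is assumed), 5 per group, 88% power.

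Power of the two-sample t-test is P(|T| > t_crit), where T is noncentral t with df = 2n − 2 and noncentrality δ = (difference / SD) × √(n/2).

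- Reproducing the plan's figure with n = 5, SD = 5.7: δ = (13 / 5.7) × √2.5 = 3.61, t_crit = 2.306 on 8 df, power = 88%.
- With n = 10 and the same SD, power is 99.8%, in line with the plan's 100%.
- The same SD gives only about 26% power at 2 per group, which the plan calls adequate. The SD therefore rests on the 88% and 100% statements, not on that one.

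Now set the true difference to zero and let a bias b shift the observed difference. The rejection probability is then the false-positive rate. Equal arms are assumed: 20/2 = 10 or 22/2 = 11, since the protocol gives both totals.

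| SD (min) | Bias (min) | δ at n = 10 | False-positive rate, n = 10 | n = 11 |
|---|---|---|---|---|
| 5.7 | 1 | 0.39 | 6.6% | 6.8% |
| 5.7 | 2 | 0.78 | 11.5% | 12.3% |
| 8 | 1 | 0.28 | 5.8% | 5.9% |
| 8 | 2 | 0.56 | 8.3% | 8.6% |
| 3 | 1 | 0.75 | 10.9% | 11.6% |
| 3 | 2 | 1.49 | 29.2% | 31.9% |

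The bias of 1 to 2 min has no source in the documents. It is an assumption chosen to show sensitivity.

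**The case against.** A reader might infer that upcoming assignments are open to the people who enrol. The documents do not support that, for four reasons:

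- The holder's name is removed, so overlap with the three consenting roles is plausible but not shown. The masking is not a fault in the plan.
- The file is password-protected, and who has the password is not stated.
- No section says that a list of future assignments exists. The generator might be run per patient after eligibility, and the stored information might be a record of assignments already made.
- If the holder does enrol patients, that shows possible access for one person, not for everyone who enrols.

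A reader might also infer that recruiters could steer patients with longer or deeper wounds into one arm. The protocol's own timing rules that out (step 2). Incision length and depth are also recorded, so an imbalance in them would be visible.

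On scale, 1 to 2 min is 8% to 15% of the planned 13-minute effect (1/13 and 2/13). A bias of that size could not by itself create the effect the trial expects.

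All of this stands. It limits the claim to what the plan fails to prevent. It does not remove the gap, because concealment has to be established by the protocol and no section does so. It also leaves untouched the fact that the surgeon may know the arm before the incision.

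**Conclusion.** The point holds as a gap in design: the plan describes no allocation concealment, does not separate custody of the allocation from enrolment, and does not delay release of the assignment. Whether anyone would in fact see or use an upcoming assignment cannot be determined from the documents.

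The possible consequence is bias in the primary endpoint of a small, single-surgeon trial in which the operator cannot be blinded. Its size cannot be derived. The illustrated rise in the false-positive rate, from 5% to about 7% to 12%, depends on an SD of about 5.7 min inferred from the plan's power statement, a two-sided t-test, equal arms of 10 to 11, and an assumed bias of 1 to 2 min. The corresponding range is about 6% to 9% if the SD is 8 min and about 11% to 32% if it is 3 min. The change is worth making mainly because it closes both routes at very little cost.

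**What to change.** Amend Randomization and blinding, Prospective Randomized Design, and Storing Documents Electronically to state that:

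1. The sequence is generated once, in advance, by someone who does not screen, obtain consent or operate (a department administrator, for example). The allocation ratio and any blocking are documented where enrolling staff cannot see them.
2. That person places the assignments in sequentially numbered, opaque, sealed envelopes and keeps the electronic list without access for the three listed roles or the surgeon.
3. The circulating nurse opens the next envelope only once consent is on file and incision length and depth are recorded, immediately before the surgeon announces the start of closure, and notes the envelope number and time.

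This fits the existing workflow, because wound dimensions are already measured before closure and the nurse already runs the stopwatch. The cost is a set of envelopes and a short protocol edit. The downside is that both closure kits must be available in the room for every case. The change does not blind the surgeon during the timed closure, so that limitation remains. If a concealment procedure already exists in practice, writing it into the protocol costs almost nothing, but release should still be moved to after the wound measurements.
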